3.6 Trial Steering Group

The TSG is composed of relevant members of the CDD Study Team (including at least one CDD member with the appropriate expertise in the area being discussed), the Chief Investigator (CI), the Chief Scientific Investigator and Principal Investigators (PIs) (a nominated sub- or co-investigator may attend in the PI or CI's place if necessary). The TSG is responsible for reviewing safety and efficacy data on a regular basis and for making decisions on dose escalation, cohort expansion/termination and other aspects of the study. Members should attend dose review meetings (in person or by telephone) and other relevant meetings. Clinical and preclinical immunology/allergy experts are involved, as needed.

Within this protocol there are various examples of when the TSG will be consulted – their involvement is not limited to these situations.

4 PATIENT SELECTION

4.1 Eligibility criteria

The patient must fulfil the eligibility criteria (listed in Sections 4.1.1 and 4.1.2). Please also note excluded concomitant medications ([Section 5.7](#)).

4.1.1 Inclusion criteria

1. Histologically or cytologically-proven advanced, unresectable solid tumour of a type known to express FR α in a percentage of cases (see [Section 2.4.2](#)).
2. Archival tumour tissue expressing FR α (1+, 2+ or 3+ membrane staining on at least 5% of tumour cells by immunohistochemistry using the BN3.2 antibody, based on the technique described by Lawson & Scorer, 2010).
3. Advanced disease for which no alternative therapy is felt to be appropriate.
4. Measurable disease or disease evaluable by tumour marker. Measurable disease is preferred for patients entering higher cohorts to facilitate efficacy assessments.
5. World Health Organisation (WHO) performance status of 0 or 1 (Appendix 1) and a life expectancy of at least 12 weeks.
6. Haematological and biochemical indices within the ranges shown below. These measurements should be performed within 7 days before the first dose of MOv18 IgE (Day -7 to Pre-dose on Day 1). Measurements performed before Day -7 may be accepted by the CDD to demonstrate eligibility if repeat testing is logistically difficult for the patient and is not considered necessary medically in the opinion of the Investigator or CDD.

Laboratory Test	Value required
Haemoglobin (Hb)	≥ 9.0 g/dL
Absolute neutrophil count	$\geq 1.5 \times 10^9$ /L
Platelet count	$\geq 100 \times 10^9$ /L
Serum bilirubin	$\leq 1.5 \times$ upper limit of normal (ULN)
Alanine aminotransferase (ALT) and aspartate aminotransferase (AST)	$\leq 2.5 \times$ ULN unless raised due to liver metastases in which case up to 5 x ULN is permissible
Serum creatinine	$\leq 1.5 \times$ ULN

7. Aged 16 years or over at the time consent is given.
8. Written (signed and dated) informed consent and capable of co-operating with treatment and follow-up.

4.1.2 Exclusion criteria

1. Radiotherapy (except for palliative reasons), endocrine therapy, immunotherapy or chemotherapy during the previous four weeks (six weeks for nitrosoureas and mitomycin-C). Investigational medicinal products during the previous 4 weeks, or 5 product half-lives before treatment.
2. Patients on beta-blockers and unable to interrupt beta-blockade (which may counteract the therapeutic effects of adrenaline), or tricyclic anti-depressants/MAOIs (which can dangerously augment the effects of adrenaline). These agents should be discontinued at least 4 half-lives before administration of the first dose of MOv18 IgE and for the duration of MOv18 IgE therapy.
3. Patients on bisphosphonates or treated with bisphosphonates in the last 18 months.
4. Ongoing toxic manifestations of previous treatments that have not resolved to Grade 1 or lower (other than alopecia of any grade or Grade 2 peripheral neuropathy).
5. Known brain metastases that have not been previously treated and been stable for at least 2 months.

6. Female patients who are able to become pregnant (or already pregnant or lactating). However, those female patients who have a negative serum or urine pregnancy test before enrolment and agree to either sexual abstinence* or to use two highly effective forms of contraception (oral, injected or implanted hormonal contraception and condom; have an intra-uterine device and condom; diaphragm with spermicidal gel and condom) effective at the first administration of IMP, throughout the study and for six months afterwards are considered eligible.
7. Male patients with partners of child-bearing potential (unless they agree to take measures not to father children by using one form of highly effective contraception at the first administration of IMP, throughout the study and for six months afterwards) or agree to sexual abstinence*. Men with pregnant or lactating partners should be advised to use barrier method contraception (for example, condom plus spermicidal gel) to prevent exposure to the foetus or neonate.
8. Major thoracic or abdominal surgery from which the patient has not yet recovered.
9. At high risk from the effects of anaphylaxis because of non-malignant systemic disease including active uncontrolled infection, cardiac failure, peripheral vascular disease, previous cerebrovascular accident (CVA), dyspnoea due to heart failure, extensive lung metastases, significant pleural effusions or other conditions.
10. History of laryngeal oedema, uncontrolled or high-risk asthma (according to Global Initiative for Asthma (GINA) guidelines – see Appendix 7), or anaphylaxis. Patients with a history of hypersensitivity to carboplatin, taxanes, or contrast media may enter the study at the investigator's discretion.
11. Patients with any congenital or acquired immunodeficiency syndrome or receiving immunosuppressive therapy (including any dose of systemic corticosteroids), or who are immunosuppressed post organ transplant. However, patients receiving inhaled corticosteroids and patients with a history of allergy (other than anaphylaxis) are eligible, as are patients with a history of auto-immune disease.
12. Known to be serologically positive for hepatitis B, hepatitis C or human immunodeficiency virus (HIV).
13. Patients with baseline elevation in serum tryptase (indicating possible mastocytosis) or a positive baseline basophil activation test (indicating a hypothetical potential for anaphylaxis with MOv18 IgE).
14. Participating or planning to participate in another interventional clinical trial, whilst taking part in this study. Participation in an observational study or in the follow-up phase of a previous interventional trial is acceptable.
15. Any other condition which in the Investigator's opinion would not make the patient a good candidate for the clinical study.
16. Patients unwilling or unable to interrupt antihistamines (which may interfere with skin prick testing). Antihistamines should be discontinued at least 4 half-lives before the first skin prick test (see Section 5.7 for further information).

* Abstinence is only considered to be an acceptable method of contraception when this is in line with the preferred and usual lifestyle of the patient. Periodic abstinence (e.g., calendar, ovulation, symptothermal, post-ovulation methods) and withdrawal are not acceptable methods of contraception.

4.2 Patient enrolment

Before enrolling the patient in the trial, the Investigator or designated representative should determine the eligibility of the patient. Please ensure that CDD are notified of any eligibility concerns at least four working days before treatment is planned. Importantly, for this trial, paired pre-treatment and on-treatment tumour biopsies are required for all patients.

Eligible patients must be enrolled in the EDC system by site staff and then registered at the CDD before they start treatment with MOv18 IgE. If the patient is eligible the patient number will be automatically allocated by the EDC system during the enrolment process. The CDD will send confirmation of the patient registration and the assigned dose level to the Investigator following enrolment of the patient. Study treatment may only be administered after confirmation has been received.

5 TREATMENT

5.1 Selection of the Phase I starting dose

In selecting the starting dose and dose escalation scheme for this trial the needs of patient safety were balanced with the desire for anti-tumour efficacy. The starting dose of MOv18 IgE was based on data from a range of sources.

- **Non-clinical studies of rMOv18 IgE**

A large block of text has been completely redacted with black bars.

[figure not shown]
- **The affinity of MOv18 IgE for the FR α**

A large block of text has been completely redacted with black bars.

- **The affinity of MOv18 IgE for the Fc ϵ RI**

A large block of text has been completely redacted with black bars.

- **Normal levels of circulating IgE in healthy humans**

A large block of text has been completely redacted with black bars.

- **Based on previous human experience**

A large block of text has been completely redacted with black bars.

Based on these data the starting dose for this clinical trial could lie in the range 10 µg to 500 mg/kg. However, the pharmacology of IgE suggests that adverse events are most likely to result from the interaction of IgE with effector cells rather than the free antibody or antibody-antigen complex. Therefore, an appropriate starting dose should consider the interaction of the IgE with Fc ϵ RI rather than its antigen interactions. As the administered IgE will have to compete with endogenous IgE for effector cell binding, the relative concentration of the two IgEs in serum is considered critical in determining the

effect of MOv18 IgE doses. Accordingly, the clinical starting dose for this study is based on the normal range of circulating IgE. A starting dose of 70 µg or one tenth of the normal circulating IgE level has been selected. A dose of 70 µg of MOv18 IgE is expected to produce a pulse of binding to effector cells before the unbound MOv18 IgE is cleared (IgE has a plasma half-life of 2 days in human). In contrast, endogenous IgEs will continuously be replenished and quickly out-compete MOv18 IgE for effector cell binding.

The 70 µg starting dose is considered to be scientifically justified based on the known pharmacology of IgE in humans. This starting dose is approximately half that estimated based on the affinity of MOv18 IgE for its target antigen, 50 fold higher than that based on its affinity for Fc ϵ RI, and six fold greater than the existing human experience of exogenously administered IgE. However, exceeding these lower estimates for the starting dose of MOv18 IgE is considered justified for MOv18 IgE based on existing knowledge of the biology of IgE.

5.2 Selection of the maximum dose

A maximum evaluated dose of 50 mg is proposed. While this dose is lower than that for most IgGs used therapeutically in oncology (e.g., trastuzumab, rituximab, bevacizumab and pertuzumab), the pharmacology of IgE indicates that these doses are sufficient to overwhelm endogenous IgE and produce pharmacodynamic effects.

5.3 Dosing schedule/treatment schedule

Please refer to Figure 3 later in this section for details of the MOv18 IgE dosing schedule.

It is planned that all patients will receive flat doses of MOv18 IgE, without adjustment for body weight or surface area (based on the expected pharmacokinetics and toxicity of an IgE, there is no reason to adjust dosing for body weight or surface area). However, a switch to weight-based dosing, and/or intra-patient escalation will be considered during the course of the trial, if emerging clinical data suggest that this could be beneficial, for example by reducing any large inter-patient variations in PK.

Initial Treatment Period

[figure not shown]
Patients in all cohorts will receive a total of six doses of MOv18 IgE at 1-week intervals unless dose-limiting toxicity is encountered or the patient develops progressive disease. During this period, three weekly doses will be considered one cycle of treatment.

A weekly dosing schedule has been selected for initial dosing of MOv18 IgE due to the relatively short plasma half-life of IgE (2 days) but relatively long tissue half-life (2 weeks). In addition, weekly dosing appeared to be efficacious in the rat model. Weekly administration should result in plasma levels sufficient to maintain occupancy of effector cell Fc ϵ RI by MOv18 IgE at higher doses.

Maintenance Period

Should additional drug supply become available during the study (for example, if dose escalation does not proceed through all the planned dose levels), patients in any cohort who appear to be benefitting from MOv18 IgE may be given up to three further doses of MOv18 IgE at fortnightly intervals continuing at the same dose level as the last administered dose (unless dose-limiting toxicity is encountered or the patient develops progressive disease). Ideally, the first maintenance dose of MOv18 IgE will be given two weeks after the sixth dose of MOv18 IgE. However, a gap of up to 4 weeks will be allowed.

A two-weekly dosing schedule has been selected for 'maintenance' dosing (which will only take place if drug supply permits). This choice is based on the expected long tissue half-life of MOv18 IgE which suggests that six weekly doses will have effectively 'loaded' the patient with MOv18 IgE-bound to effector cells in the tissues.

Figure 3: MOv18 IgE Dosing Schedule

5.3.1 Study drug administration

All patients will receive their first two doses of MOv18 IgE as an IV infusion over 90 minutes (+/-15 mins). A shorter infusion time for subsequent doses of 60 minutes (+/-10 mins) will be allowed if no infusion-related reactions or other allergic reactions are encountered after two doses have been administered. A longer infusion time for subsequent infusions will also be allowed if required in order to manage infusion related cutaneous toxicity. Patients should remain in the clinic for observation for at least one hour after every dose of MOv18 IgE.

The study will be undertaken at investigational centres staffed and equipped to manage medical emergencies and with intensive care facilities. If the patient experiences an event related to study drug that requires intensive clinical care, the Sponsor must be notified immediately.

Patients will be admitted overnight after the first two doses to facilitate intensive safety monitoring procedures. At the investigator's discretion, the requirement for admission may be waived for the second dose if the patient experiences no clinically important adverse events related to MOv18 IgE during the infusion and observation period.

Pre-medication will be administered prior to the first dose in later cohorts if deemed medically appropriate. See Section 5.4

The patient will be intensively monitored during their first two infusions, with measurement of vital signs (blood pressure, pulse rate and temperature) every 15 minutes from the start of the infusion until 30 minutes after completion of the infusion. If no changes are seen, during the first two infusions, then for subsequent infusions vital signs will be assessed 15 minutes and 30 minutes after completion of the infusion. Continuous monitoring with a pulse oximeter is required throughout each infusion until 30 minutes after completion.

If the patient experiences symptoms suggestive of an infusion-related reaction or cytokine release (such as fever, chills, and myalgia), the infusion must be slowed or interrupted and the patient must be treated with oxygen, paracetamol, antihistamines, fluid resuscitation and/or steroids, as clinically indicated. If the reaction does not respond to these conservative measures or is > Grade 2 in severity, the algorithm for the treatment of anaphylaxis must be followed (Appendix 4). Note that for the purposes of this protocol, infusion-related symptoms and signs (such as fever, myalgia, and hypotension) will be recorded and graded individually according to NCI-CTCAE Version 4.02. Grading of systemic mast cell degranulation (anaphylaxis) is defined in Appendix 5 and grading of cytokine release syndrome is defined in Appendix 6, but the distinction between these two events and grading of these events will be performed only in retrospect when results of serum tryptase assays are available, and will thus not be relevant for the management of acute events at the time of infusion. A blood test for measurement of serum tryptase will be taken on completion of all infusions. Additional blood samples for serum tryptase levels should be taken in patients who experience a suspected anaphylactic reaction, such as urticaria and/or severe infusion-related symptoms necessitating interruption or discontinuation of the infusion. Additional samples for serum tryptase should also be taken for patients with a positive skin prick test (see study lab manual and protocol section 7.2 for time points). For details on grading and reporting of infusion-related events and anaphylaxis see Section 7.2.5.

The following medications must be available at the bedside for use in case of an immune-mediated reaction: epinephrine (0.5-1mL IM injection 1:1000), chlorphenamine 10 mg IV/IM injection, paracetamol 1 g orally, hydrocortisone 200 mg IM or IV; oxygen (see 16.4 Appendix 4: Treatment of Anaphylaxis).

For patients who are enrolled in an intra-patient escalation cohort, and receive a higher dose in Cycle 2, the following additional measures will apply:

- In Cycle 1 and in Cycle 2 all patients will receive their first two doses of MOv18 IgE as an IV infusion over 90 minutes (+/-15 mins). A shorter infusion time for subsequent doses of 60 minutes (+/-10 mins) will be allowed if no infusion-related reactions or other allergic reactions are encountered after two doses at each dose level have been administered. A longer infusion time for subsequent infusions will also be allowed if required in order to manage infusion related cutaneous toxicity.
- Patients will be admitted overnight after the first two doses in Cycle 1, and the first two doses in Cycle 2 to facilitate intensive safety monitoring procedures. The requirement for admission may be waived for the second dose in each cycle at the investigator's discretion.
- Patients will be intensively monitored during their first two infusions (Cycle 1 doses 1 and 2) and in Cycle 2 (doses 4 and 5 at the increased dose level), the same monitoring will be performed as for Cycle 1.

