16.4 Appendix 4: Treatment of Anaphylaxis

[Based on (Simons et al., 2011a; Simons et al., 2011b)]

If the patient experiences symptoms suggestive of an infusion-related reaction or cytokine release, the infusion must be slowed or interrupted, and the patient must be treated with oxygen, paracetamol, antihistamines, fluid resuscitation and/or steroids, as clinically indicated.

Anaphylaxis should be suspected if:

- There is a sudden onset and rapid progression of symptoms
- The reaction is > Grade 2 in severity (see Appendix 5) and fails to respond to the conservative measures outlined above

or

- The reaction is > Grade 2 in severity and associated with rapid onset of urticaria (within 10 minutes of starting the infusion).
- The patient experiences life-threatening airway and/or breathing and/or circulation problems

If anaphylaxis is suspected based on these criteria:

- Summon help (resuscitation team)
- Stop the infusion
- Inject epinephrine (adrenaline) intramuscularly into the mid-anterolateral aspect of the thigh
 - 0.5-1mL 1:1000 epinephrine
 - Record the time of dose and repeat it in 5-15 minutes if needed (e.g. because of progressing hypotension and/or laryngeal oedema).
- Place the patient on his/her back or in a position of comfort if there is respiratory distress and/or vomiting; elevate the legs
- If not already started, give high-flow (6-8 L/min) supplemental oxygen by face mask
- If not already started, give 1-2 litres of 0.9% isotonic saline rapidly (e.g. 5-10 mL/kg in the first 5-10 minutes), as clinically indicated
- Give chlorphenamine 10mg IM or slow IV
- Consider hydrocortisone 200mg IM or slow IV
- Consider bronchodilators if clinically indicated.

Cardiac arrest associated with anaphylaxis

- If indicated, perform cardiopulmonary resuscitation as per Adult Life Support guidelines

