16.5 Appendix 5: Trial-specific Grading of IgE-associated Mast Cell Degranulation (anaphylaxis)

Grade 1	Grade 2	Grade 3	Grade 4	Grade 5
No infusion-related symptoms or mild symptoms not requiring treatment, in the presence of a positive serum tryptase assay	Therapy or infusion interruption indicated but responds promptly to symptomatic treatment (e.g. antihistamines, NSAIDS, IV fluids), in the presence of a positive serum tryptase assay	Prolonged and/or severe symptoms with hypotension (systolic BP < 100 mmHg) and/or angioedema, laryngeal oedema, bronchospasm or hypoxia* (sats <92% on room air), in the presence of a positive serum tryptase assay	Life-threatening consequences (pressor or ventilatory support indicated), in the presence of a positive serum tryptase assay	Death

** - for patients with lung metastases whose baseline saturations on air may be significantly lower than 100%, hypoxia is defined as a drop in saturations requiring the administration of oxygen*

In general, rapid onset of urticaria suggests mast cell degranulation (anaphylaxis) rather than cytokine release syndrome. However, urticaria alone appears to be a common but manageable symptom of MOv18 IgE infusion.

Note: for this study, a positive serum tryptase assay is required for infusion-related events to be ascribed to IgE-associated mast cell degranulation (anaphylaxis).

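### Section 5.3.1 and Appendix 4 give different triggers for the anaphylaxis treatment algorithm, and Appendix 4 ties its bedside grade to a tryptase-dependent scale

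*Protocol*

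**What the plan says.** **Section 5.3.1 (Study drug administration).** Reactions suggestive of an infusion reaction or cytokine release are first managed by slowing or interrupting the infusion and giving supportive treatment. The rule then applies if a reaction of this kind "does not respond to these conservative measures or is > Grade 2 in severity, the algorithm for the treatment of anaphylaxis must be followed"; the reference given is to Appendix 4. Either condition is enough, and the instruction is mandatory. The same paragraph says that telling anaphylaxis from cytokine release, and grading either, is "performed only in retrospect when results of serum tryptase assays are available, and will thus not be relevant for the management of acute events".

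**Appendix 4 (Treatment of Anaphylaxis).** After the same conservative measures, four circumstances are listed in which anaphylaxis should be suspected:

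- sudden onset with rapid progression, at any grade;
- severity plus non-response, worded as "The reaction is > Grade 2 in severity (see Appendix 5) and fails to respond to the conservative measures outlined above";
- severity plus early urticaria, worded as "The reaction is > Grade 2 in severity and associated with rapid onset of urticaria (within 10 minutes of starting the infusion");
- a threat to life, worded as "The patient experiences life-threatening airway and/or breathing and/or circulation problems".

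The action steps, which include stopping the infusion and giving intramuscular epinephrine, open with "If anaphylaxis is suspected based on these criteria".

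**Appendix 5 (trial-specific grading).** Grade 3 begins "Prolonged and/or severe symptoms with hypotension (systolic BP < 100 mmHg) and/or angioedema, laryngeal oedema, bronchospasm". Life-threatening consequences are a separate Grade 4. Grades 1 to 4 each require a positive tryptase, and the closing note repeats that "a positive serum tryptase assay is required for infusion-related events to be ascribed to IgE-associated mast cell degranulation (anaphylaxis").

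**The concern.** This is the emergency rule for the first risk listed in Section 9, in a multi-centre first-in-human trial that is still escalating. A site that follows 5.3.1 and a site that follows Appendix 4 can reach different answers about the same patient.

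The cross-referencing makes this more likely. Section 9 sends the reader to Sections 7.2.1 and 7.2.5 and Appendix 4 for management of reactions, and does not name 5.3.1. Section 7.2.5 contains no treatment trigger, and 7.2.1 cites 5.3.1 only for how often vital signs are taken. A clinician who follows that pointer may never meet the 5.3.1 rule.

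The scale adds a second difficulty. Appendix 4 asks for a bedside grade from a table that 5.3.1 reserves for later classification. Section 5.3.1 names no scale for its own threshold, and its next sentence grades individual symptoms by CTCAE. The same cut-off could therefore be read on two scales.

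**Working it through.** No figure in the protocol is involved, so this is a comparison of rules.

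**Inputs.** G: reaction above Grade 2. U: does not respond to conservative measures. S: sudden onset with rapid progression. R: urticaria within 10 minutes of starting the infusion. L: life-threatening airway, breathing or circulation problem. The Appendix 4 bullets are read as alternatives; the appendix prints only one connecting *or*, between the second and third.

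**Rules.**

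- Section 5.3.1: G or U.
- Appendix 4: S, or (G and U), or (G and R), or L.

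**Comparison.**

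| Reaction | Section 5.3.1 | Appendix 4 |
|---|---|---|
| G, U; no S, R, L | required | listed |
| G, responds; no S, R, L | required | not listed |
| Not G, U; no S, R, L | required | not listed |
| Not G, responds; no S, R, L | not required | not listed |
| G, responds, R | required | listed |
| Not G, U, R | required | not listed |
| Not G, responds, S | not required | listed |

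With none of S, R or L present, the rules disagree in 2 of the 4 combinations of grade and response. Early urticaria closes the gap for the reaction above Grade 2 but not for the lower-grade unresponsive one. Sudden onset closes both gaps and opens one in the other direction (last row). L without G is not tabulated, because Appendix 5 places life-threatening events at Grade 4.

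**Can the disputed rows occur?**

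- *Above Grade 2, responsive.* Grade 2 in Appendices 5 and 6 is defined by prompt response to symptomatic treatment, so a reaction above Grade 2 has usually not responded promptly. The row survives because Appendix 5 Grade 3 covers prolonged **and/or** severe symptoms: for example, a fall in systolic pressure below 100 mmHg that recovers with fluids.
- *Grade 2 or less, unresponsive.* For the same reason this row is thin on the trial's own scales. Appendix 6 puts a reaction that is not rapidly responsive at Grade 3. Under Appendix 5, the scale Appendix 4 cites, a prolonged reaction without hypotension or another named sign meets neither Grade 2 nor Grade 3. On CTCAE grades for individual symptoms, persistent Grade 2 symptoms fit the row directly.
- *Grade 2 or less, responsive, sudden onset with rapid progression.* Nothing in the grade definitions excludes it.

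**Scale.** Appendix 4 cites Appendix 5 for the grade. Appendix 5 Grades 1 to 4 require a positive tryptase. Section 5.3.1 says the tryptase-based grading is retrospective and has no role in acute management. Taken literally, the grade that Appendix 4 asks for cannot be assigned when it is needed. The clinical descriptors (blood pressure, oxygen saturation, bronchospasm, angioedema) can be judged at once, but no section says to use them without the assay.

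**The case against.** The strongest reply is that both texts can be obeyed. Following the Appendix 4 algorithm can mean entering at its criteria for suspecting anaphylaxis, so that 5.3.1 only sends the clinician there. Appendix 4 also says when anaphylaxis should be suspected, not that it should be suspected only then. This has some force: on that reading, the severity limb of 5.3.1 still prompts a check for early urticaria, rapid progression and life-threatening signs. But 5.3.1 does not say that it means assessment; it makes the treatment algorithm mandatory, and Appendix 4 makes its actions conditional on its own list.

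It is also fair that the disputed cases are few, that infusion staff are likely to read the drug-administration section, and that centres have intensive care facilities, continuous oximetry during infusion and epinephrine at the bedside. These points limit the size of the problem without removing the inconsistency.

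Three stronger readings are not supported:

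- *That treatment must wait for tryptase.* A reader might infer this from the Appendix 5 reference and from Table 4 footnote (h), which schedules some results for reporting before the next dose. Section 5.3.1 rules it out by taking that grading out of acute management.
- *That Appendix 4 is simply the narrower rule, so copying 5.3.1 into it would be enough.* Appendix 4 has an any-grade trigger for sudden, rapidly progressing reactions that 5.3.1 lacks. Copying 5.3.1 alone would delete it.
- *That Appendix 4 forbids treating a severe reaction that responds.* It leaves the case unlisted; it does not prohibit treatment.

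**Conclusion.** The inconsistency is real and rests on the current text alone. The two triggers differ in three kinds of reaction: two are mandatory only under 5.3.1 and one is caught only by Appendix 4. The bedside grade in Appendix 4 points to a scale that 5.3.1 says is not for bedside use.

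The size is modest. The protocol gives no frequency for these reactions and none is claimed here. A reader might infer that the anaphylaxis assessment in Section 3.4.2 is affected. It is not: that assessment uses the retrospective Appendix 5 grade, which stays as it is. No endpoint, stopping rule or statistical figure changes. The issue is consistent emergency management across sites.

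The conclusion assumes that the Appendix 4 bullets are alternatives and that following the algorithm in 5.3.1 means carrying out its treatment steps. If the sponsor meant only assessment under Appendix 4, the first two mismatches become a matter of unclear wording. The sudden-onset mismatch and the scale problem remain.

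**What to change.** State one trigger list, in identical words, in Section 5.3.1 and Appendix 4, as the union of the two. The algorithm is followed if the reaction:

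1. fails to respond to conservative measures; **or**
2. is above Grade 2; **or**
3. has sudden onset with rapid progression; **or**
4. involves life-threatening airway, breathing or circulation problems.

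The early-urticaria criterion is then covered by item 2. The list needs the sponsor's clinical confirmation. If 5.3.1 was meant only to start assessment under Appendix 4, it should say so.

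In both places, define above Grade 2 at the bedside by the Appendix 5 clinical descriptors irrespective of tryptase, and leave the retrospective tryptase-based classification unchanged. Add Section 5.3.1 to the pointer in Section 9.

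The cost is protocol wording and a notice to sites, with no effect on data or sample size. The small clinical downside is that some severe reactions already responding to conservative measures would receive epinephrine.
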